5.8 Data Quality and Monitoring Measures

As much as possible data quality is assessed at the data entry point using intelligent online data entry. Data element constraints, whether independent range and/or format limitations or 'relative' referential integrity limitations, can be enforced by all methods employed for data input. QA reports assess data quality post-data entry. As we note, data quality begins with the design of the data collection forms and procedures and incorporates reasonable checks to minimize transcription and omission errors. Of the more important quality assurance measures are the internal validity checks for reasonableness and consistency.

- Data Monitoring: The DMCC identifies missing or unclear data and generates a data query to the consortium administrator contact.
- Data Delinquency Tracking: The DMCC will monitor data delinquency on an ongoing basis.

5.9 Quality Control: Study Related Procedures

Study related procedures will be outlined in a Manual of Operations (MOO), which will be distributed to each of the study sites. The MOO will include descriptions of methods for blood collection, processing and storage. Instructions will be included for shipment of specimens to the Study Chair for batch shipment to reference laboratories for testing.

6. Statistical Considerations

Data from this study will be submitted to the DMCC located at the Cincinnati Children's Hospital & Medical Center. Physical examination, laboratory studies, vital signs, and growth parameters assessed at week 0 and week 8 will be tabulated. The difference in total serum cholesterol, 7-DHC and 8-DHC, sterol ratio, oxysterol levels, serum bile acids, and liver function from the baseline visit (week 0) to week 8 visit will be calculated for each participant. The average change and 95% confidence intervals for each of these measurements will be estimated.

Safety data will be summarized for all treated subjects using appropriate tabulations, and descriptive statistics. The incidence rate of each adverse event will be estimated and reported with exact 95% confidence intervals.

Sample size: This pilot study is intended to explore preliminary signals for efficacy as well as examine safety of cholic acid supplementation. The primary purpose of the study is to detect a difference in pre-and-post treatment mean serum cholesterol level of one group. The sample size was based upon a sufficient number of participants to begin such explorations prior to pursuit of a randomized controlled trial and historical variation in serial serum cholesterol levels in SLOS subjects. We conservatively use the population effect size of 0.80 and the significance level (alpha) of 0.05 using a two-sided one-sample t-test. With an accrual of 13 evaluable participants, an estimated standard deviation of 5 mg/dl with mean 61 mg/dl for the cholesterol measurements, a within subject correlation of .8 (between pre and post testing) and a two-sided alpha of 0.05, there is greater than 80% power to detect a change in total serum cholesterol of greater than 10 mg/dl. Under the same assumptions, for sterol ratio of 7-DHC/cholesterol, based on a standard

deviation of 0.21, there is greater than 80% power to detect a change of greater than 0.07. To adjust for 15% dropout rate, 15 SLOS patients will be recruited for the study. There will be no interim analysis of the data.

7. Data Management

The following data will be obtained:

- Demographics: age (years and months), date of birth, gender.
- Physical measurements, including vital signs, weight, height, blood pressure.
- Laboratory: serum cholesterol, 7-DHC, 8-DHC, oxysterols, serum bile acids (total bile acids, cholic acid, chenodeoxycholic acid, comprehensive chemistry profile (including AST, ALT, bilirubin), GGT and complete blood count (CBC) including platelets.

All study data will be collected via systems created in collaboration with the DMCC and will comply with all applicable guidelines regarding patient confidentiality and data integrity.

All research data will be collected on data forms and submitted online to the DMCC REDCap database. Participant identifiers will be used to protect participant confidentiality and safety.

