Statistician:	University of Nebraska Medical Center, TBD			
Consortium:	Sterol and Isoprenoid Research Consortium (STAIR)			
Participating Sites:	Children's Hospital Colorado			
	University of Nebraska Medical Center			
Activation Date:	TBD			
Current Status:	NIH and DSMB Approved			
Sample Size:	Up to 15 enrollees with expectation to have 12 evaluable subjects			
Target Enrollment Period:	September 2020- May 2021			
Study Design:	Open-label, multi-center, pilot study			
Primary				
Objectives:	serum cholesterol and related sterol biomarkers (7- and 8-			
	dehydrocholesterol) in subjects with Smith-Lemli-Opitz			
	syndrome (SLOS).			
	2. Examine the safety of cholic acid administration to			
Cocondon	subjects with SLOS by measuring adverse events.			
Secondary Objectives:	1. Determine the effect of cholic acid supplementation on serum oxysterol levels, serum bile acids, and vitamin D in			
Objectives.				
Exploratory	subjects with SLOS. 1. Serum bile acid levels.			
Outcome	2. Changes in safety monitoring tests including liver			
Measures:	function as determined by serum transaminases, bilirubin,			
mododi ooi	albumin, alkaline phosphatase, GGT and CBC.			
Study Population	Subjects will be recruited through referrals from			
and Main	physicians at participating STAIR sites and subject			
Eligibility/	referrals from the SLOS/RSH Foundation.			
Exclusion Criteria:				
	Main Eligibility Criteria include:			
	Parent/Guardian provide written consent.			
	1. Talent Gaardian provide written consent.			
	Subject has biochemically and genetically			
	Subject has biochemically and genetically confirmed diagnosis of SLOS.			
	 Subject has biochemically and genetically confirmed diagnosis of SLOS. Subject is ages 2-28 years at enrollment. 			
	 Subject has biochemically and genetically confirmed diagnosis of SLOS. Subject is ages 2-28 years at enrollment. Subject's serum cholesterol ≤125 mg/dL prior to 			
	 Subject has biochemically and genetically confirmed diagnosis of SLOS. Subject is ages 2-28 years at enrollment. Subject's serum cholesterol ≤125 mg/dL prior to enrollment. 			
	 Subject has biochemically and genetically confirmed diagnosis of SLOS. Subject is ages 2-28 years at enrollment. Subject's serum cholesterol ≤125 mg/dL prior to 			

	6. Subject is able to travel to one of the STAIR sites.		
	Main Exclusion Criteria include:		
	Subject is clinically unstable.		
	 Subject is unlikely to complete the study, in the 		
	opinion of the investigator.		

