	3. Subject is taking drugs, nutraceutical, probiotics or		
	other compounds that are known or suspected to		
	lower serum cholesterol.		
	4. Subject has transaminase elevations > 3-fold		
	above the reference range at enrollment.		
	5. Subject is pregnant or likely to become pregnant.		
	Treatment (if applicable)		
Agent:	Cholic acid (trade name Cholbam®; Retrophin, Inc.)		
Dosage, Schedule,	10 mg/kg/day, divided BID, administered either orally or		
Route of	via J- or G-Tube with a treatment duration of 2 months		
Administration:	Although proviously administered to SLOS subjects, shalis		
Safety Issues:	Although previously administered to SLOS subjects, cholic acid has an undefined safety profile in SLOS subjects. In		
	subjects with other disorders of cholesterol metabolism		
	(Zellweger spectrum disorder and inherited single enzyme		
	diseases of bile acid synthesis), worsening liver		
	transaminases have been documented in a minority of		
	treated subjects. These diseases are marked by inherent		
	liver abnormalities prior to treatment. Due to the potential		
	for worsening liver toxicity while on treatment with cholic acid, participants will be closely monitored for		
	hepatotoxicity while on cholic acid and for one month		
	following completion of the treatment trial.		
Primary Outcome	Serum cholesterol, serum 7- and 8-dehydrocholesterol,		
Measures:	sterol ratio, and incidence of adverse events.		
Secondary	Serum oxysterol levels.		
Outcome Measures:			
Exploratory	Serum vitamin D, serum bile acids, chemistries (AST,		
Outcome	ALT, bilirubin, albumin).		
Measures:			
Statistical	The study will enroll up to 15 subjects with the aim for 13		
Considerations	evaluable subjects to complete the study.		
(sample size and			
analysis plan):	1 Notional Institute of Child Llegith and Llumes		
Sponsors (federal,	National Institute of Child Health and Human Development:		
state, foundation	Development;		

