Study Protocol: Subjects will be treated with cholic acid, either orally or via gastrostomy tube, daily for 8 weeks. Blood will be collected at enrollment (week-0), and cholic acid will be started once the cholesterol level is shown to be ≤125 mg/dL. Blood for research tests will be obtained at week-0 and week-8 of cholic acid treatment, and 4 weeks off cholic acid (week-12). An additional blood collection for safety labs only will take place every 4 weeks (week-0, week-4, week-8 and week-12), either at a STAIR site or locally as an option for subjects who live distantly from a STAIR site.

2. Specific Aims (Hypothesis and Objectives)

Smith-Lemli-Opitz syndrome (SLOS) is an autosomal recessive disorder associated with multiple congenital anomalies, intellectual disability, failure to thrive, and behavioral changes. It has an estimated prevalence of 1/20,000 to 1/40,000. Patients with SLOS have deficiency of 7-dehydrocholesterol reductase (DHCR7), an enzyme that catalyzes the last step in the cholesterol synthesis pathway. Consequently, cholesterol levels are low and precursor sterols accumulate. Since cholesterol is the initial substrate for bile acid synthesis, it is likely that bile acid production is low and dietary cholesterol is not efficiently absorbed, adding to the overall cholesterol deficiency seen in this disease. The symptoms of SLOS are thought to be a result of systemic cholesterol deficiency and accumulation of sterol precursors. Although dietary cholesterol supplementation is considered the most rational approach to treatment of SLOS, dietary cholesterol has a limited effect on serum cholesterol levels of many patients, suggesting that it is not efficiently absorbed from the diet.

As the already impaired absorption of dietary cholesterol is compounded in part by deficient bile acid production, we **hypothesize** that administering cholic acid (Cholbam®, Retrophin, Inc) orally or by a gastrostomy tube to SLOS subjects with low serum cholesterol will result in an increase in serum cholesterol and a decrease in the precursor metabolites 7- dehydrocholesterol (7-DHC) and 8- dehydrocholesterol (8-DHC).

Our **objective** is to examine whether cholic acid therapy has efficacy for improving the sterol abnormalities in SLOS. This will be determined by achieving the following Specific Aims:

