In summary, cholic acid treatment may improve intestinal cholesterol absorption in severe SLOS patients with impaired bile acid synthesis, and may also be beneficial in less severely affected patients with normal or subnormal bile acid synthesis, simply by increasing the bioavailability of supplemental cholesterol. Increasing cholesterol absorption with cholic acid would secondarily increase the systemic cholesterol level and significantly decrease the levels of toxic cholesterol precursors through feedback inhibition of the cholesterol biosynthesis pathway.

4. Study Design and Methods

This will be an open label, multi-center, pilot study to assess the effects of cholic acid administration on serum sterol levels. Up to 15 SLOS subjects will be enrolled with the expectation that 13 subjects will complete the study and provide evaluable data. Subjects must have a documented serum cholesterol ≤125 mg/dL measured within 6 months prior to enrollment to qualify for the study. Informed consent will be obtained prior to completing any study procedures. Subjects will be studied in 2 phases (see Figure 2). The first phase is a "Treatment Phase". Those subjects who have a serum cholesterol ≤125 mg/dL will be qualified to be administered cholic acid (Cholbam®, Retrophin, Inc) at 10 mg/kg/day dosages given orally or via J- or G-tube divided BID for two months (weeks 0 to 8). This dose is based on weight, even in older patients. After completion of the 8-week Treatment Phase of the study, cholic acid will be discontinued and subjects will enter the "Post-treatment Phase" for 4 weeks (weeks 9-12).

We have chosen to perform this trial in patients who fall in the moderate to severely affected range, with the hope that this will allow us to see a greater affect of cholic acid treatment. Levels of cholesterol and precursors are associated with severity of disease, with those more severe patients showing lower cholesterol levels and higher levels of precursors. Although there is some variation in these values based on dietary intake and well being of the patients (intercurrent illness can worsen cholesterol deficiency and raise precursor levels, for example), these variations are not expected to impact the ability to assess affects of treatment. A severely affected patient does not suddenly appear to be

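### The evaluable number is given as both 12 and 13, 15 recruits with 15% dropout yield 12.75, and exact power at the planning effect size of 0.80 is below 80% at either number

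*Combined protocol and SAP*

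**What the plan says.** The evaluable number appears in four places.

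- Section 1, Protocol Synopsis, Sample Size row: "Up to 15 enrollees with expectation to have 12 evaluable subjects".
- Section 1, Protocol Synopsis, Statistical Considerations row: "The study will enroll up to 15 subjects with the aim for 13" evaluable.
- Section 4, Study Design and Methods: "Up to 15 SLOS subjects will be enrolled with the expectation that 13 subjects will complete the study and provide evaluable data".
- Section 6, Statistical Considerations, sample size paragraph: "With an accrual of 13 evaluable participants", which introduces the power statements.

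On recruitment, Section 6 says "To adjust for 15% dropout rate", "15 SLOS patients will be recruited for the study".

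On the planning basis, Section 6 says "We conservatively use the population effect size of 0.80 and the significance level (alpha) of 0.05 using a two-sided one-sample t-test". It then claims more than 80% power for a cholesterol change above 10 mg/dl, using an SD of 5 mg/dl and a pre/post correlation of 0.8.

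On entry to treatment, Section 1.1 has blood drawn at enrolment (week 0), after which "cholic acid will be started once the cholesterol level is shown to be ≤125 mg/dL". Section 4.1 (criterion 6) admits subjects on a value up to 6 months old and confirms it at the first site visit.

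**The concern.** Three things do not line up. The synopsis disagrees with itself and with Section 6 on how many subjects will be analysed. The dropout allowance, taken literally, does not return the 13 on which power is stated. And the allowance is described as dropout only, while the cap of 15 is on enrolment, so a subject enrolled and then found above 125 mg/dL at week 0 would seem to use a place without ever contributing a treated change.

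In a pilot this small, one subject is about 8% of the evaluable data (1/13 = 7.7%; 1/12 = 8.3%). The evaluable number determines the width of every confidence interval the study will report. A reader should be able to tell which number the design promises and what power goes with it.

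**Working it through.** **Inputs.** Recruits 15, dropout 15%, evaluable 13, effect size 0.80, two-sided alpha 0.05, one-sample t-test, SD 5 mg/dl and correlation 0.8 all come from Section 6. The alternative evaluable number, 12, comes from the synopsis Sample Size row.

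**Reproducing the plan's figures.**

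- Recruitment of 15: 13 × (1 + 0.15) = 14.95, rounded up to 15. This matches the plan, but multiplying by 1 + d does not recover 13 once 15% are lost.
- Evaluable 13: the normal approximation for 80% power at effect size 0.80 is ((1.960 + 0.842)/0.80)² = 12.3, rounded up to 13. This may be the source of the number; the documents do not say.

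**Dropout arithmetic.**

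- Forward: 15 × (1 − 0.15) = 12.75.
- Backward: 13/(1 − 0.15) = 15.3, or 16 when rounded up. For 12 evaluable, 12/0.85 = 14.1, or 15.
- In whole subjects: losing 2 of 15 is 13.3% and leaves 13; losing 3 of 15 is 20% and leaves 12.
- If losses are independent at 15%, completers follow Binomial(15, 0.85). P(13 or more) = 60% and P(12 or more) = 82%. The median and the mode are both 13.

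**Power at effect size 0.80.** Exact power comes from the noncentral t distribution with n − 1 degrees of freedom and noncentrality 0.80 × √n.

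| n | Exact t power | Normal approximation | Effect size for 80% power (exact) |
|---|---|---|---|
| 12 | 71.4% | 79.1% | 0.89 |
| 13 | 75.4% | 82.2% | 0.85 |
| 15 | 82.1% | 87.3% | not needed here |

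The smallest n with at least 80% exact power at 0.80 is 15. Going from 13 to 12 costs 75.4 − 71.4 = 4.0 points.

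**Power for the 10 mg/dl change.** SD of change = 5 × √(2 × (1 − 0.8)) = 3.16 mg/dl, so 10 mg/dl is a standardised change of 10/3.16 = 3.16. Power is above 99.9% at n = 12 and therefore also at n = 13. The change detectable with 80% power is 0.889 × 3.16 = 2.81 mg/dl at 12 and 0.847 × 3.16 = 2.68 mg/dl at 13.

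**Week-0 failures (illustration only).** The documents give no failure rate. Assuming one of 15 enrolled subjects fails the check, 14 are treated and 14 × 0.85 = 11.9 are expected to complete.

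**The case against.** The strongest reply is that this is rounding. The expectation of 12.75 is a quarter of a subject below 13, subjects are whole, and 13 is the most likely number of completers. That stands. A reader might infer that the design delivers only 12; the plan's own dropout rate does not support this, since 13 or more is reached with 60% probability.

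A reader might also infer that slipping from 13 to 12 is what pushes power below 80%. It is not. Exact power at effect size 0.80 is already 75% at the plan's own 13. Section 6 also attaches no power value directly to 0.80: its cholesterol claim concerns a change above 10 mg/dl, and that claim is safe at either number. (The separate sterol-ratio claim has its own difficulty, which does not arise from 12 versus 13.)

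Completers are not quite the same as evaluable subjects. The efficacy change runs from week 0 to week 8, and Section 5.7 keeps data acquired before withdrawal, so a loss during weeks 9 to 12 leaves the change calculable. The binomial figures count every dropout as lost and are pessimistic to that extent.

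On week 0, no text says how failures count towards the 15. The prior qualifying value and a planning mean of 61 mg/dl, far below 125, suggest failures may be few. The ambiguity is fair to raise; its size is unknown.

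None of this removes the plain disagreement between 12 and 13.

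**Conclusion.** The point holds as an inconsistency in a planning figure, with modest consequences. The protocol states two evaluable numbers, with 12 the outlier, and its recruitment and dropout figures give an expectation between them, marginally short of 13.

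The power shortfall at effect size 0.80 is present at both numbers. It comes from reading 0.80 against an exact t-test at this sample size, and the dropout allowance changes it by only about 4 points. The claim for a 10 mg/dl change is unaffected, provided the stated SD and correlation hold.

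The completer probabilities assume independent 15% losses, each making a subject non-evaluable. The 11.9 rests on an assumed single week-0 failure and shows only that the cap needs a definition.

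**What to change.** Use one evaluable number in the synopsis, Section 4 and Section 6. Either option works:

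- **State 12.** Report 71% power at effect size 0.80, and say that 80% power needs an effect size of about 0.89.
- **Keep 13.** Describe the allowance as 2 of 15 (13.3%), report 75% power at effect size 0.80, and say that 80% power needs about 0.85.

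In either case, state that the cap of 15 counts subjects who start cholic acid, so that week-0 failures do not use up places.

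The cost is wording, a slightly less favourable stated figure, and possibly one or two extra baseline visits to replace subjects who fail the check. No more than 15 subjects would be treated.

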7.1 Registration

IRB approval for the protocol must be on file at the DMCC before accrual can occur from the clinical site.

The DMCC will use a system of coded identifiers to protect participant confidentiality and safety. Each participant enrolled will be assigned a local identifier by the enrollment site. This number can be a combination of the site identifier (location code) and a serial accession number. Only the local site will have access to the linkage between this number and the personal identifier of the subject.

7.2 Data Entry

Data collection for this study will be accomplished with online electronic case report forms. Using encrypted communication links, on-line forms will be developed that contain the requisite data fields.

7.3 Laboratory Data Flow

If possible and practical for this pilot study, the DMCC will provide laboratories with online forms and/or electronic data exchange mechanisms - depending on their capabilities and needs - to enter, update and obtain relevant data. Online forms exist to verify specimen receipt, report specimen issues and submit test results for specimens. The preferred method to exchange data electronically is through the Specimen Management System Web Service. The Web Service allows laboratories to obtain specimen shipment information, receive individual specimens or specimen shipments, report specimen issues and communicate specimen aliquots in a secure manner (test result submission is

planned). The DMCC will also support uploading of files electronically. All transactions are logged and validated for both methods.

7.4 Study Records Retention

Hard copies of data forms will be stored at each STAIR study site that enrolls subjects. Forms will be stored for at least 5 years after completion of the study.

7.5 Protocol Deviations

Protocol deviations are defined as any significant alteration of the proposed procedures. Deviations will be reported to the site PI and recorded. Protocol deviations will also need to be reported to the IRB and DMCC. Deviations will include, but are not limited to, the following:

- Failure to obtain proper written consent.
- Failure to obtain required blood specimens on time (± 5 days).
- Inadequate administration of cholic acid dose.
- Failure to return to study site visit on time (± 5 days).
- Inappropriate specimen collection, change in drug dosing or other data collection.

8. Human Subjects

8.1 Good Clinical Practice Statement

This clinical trial will be conducted in accordance with the ethical principles that have their origin in the Declaration of Helsinki, and that are consistent with Good Clinical Practice and all applicable regulatory requirements.

8.2 Benefits

Subjects will receive no clinical benefit from participating in this study. It is hoped that the information learned in this study will be able to help others with SLOS in the future.

8.3 Risks

Risks of participating in this study are summarized in Section 5.3 and consist of risks associated with cholic acid therapy, phlebotomy and potential loss of confidentiality.

8.4 Inclusion of Subjects

Since SLOS is not limited to any particular ethnic minority or socio-economic group or gender, we anticipate enrolling any and all subjects who are diagnosed and satisfy the inclusion criteria.

Inclusion of children

Because the majority of subjects with SLOS are children and relatively few adults with SLOS are known, we expect that children will be the major group studied. We will recruit subjects between 2 years to 28 years of age and of both genders.

Inclusion of women

Women and girls will be included in the study. SLOS is an autosomal recessively inherited condition that affects males and females equally, so females should be equally represented in this study. However, since this disorder is uncommon, STAIR investigators will have limited control over the gender mix of the study population.

Inclusion of Minorities

SLOS affects all ethnic and minority groups. Owing to the rarity of SLOS in the United States population, STAIR investigators will have limited control over the race and ethnicity mix of the study population. In order to increase the enrollment of minority subjects, we will recruit from a national population, so that subjects in all regions of the U.S. with ethnically and racially diverse populations may be recruited.

